Appendix N: Operative Steps

Operative Steps

	Investigator	Coordinator/Surgical Associate
1		
a. Assure all necessary equipment are present and ready for use, including:
 
  Writing utensil with indelible ink;  Calibrated mass balance (readability and repeatability in milligrams, 0.001 g);  Timing device (precision in seconds);  Millimeter incremented tool;  Study Devices (2 packaged 5g bellows of PerClot and 2 packaged 5g bellows of Arista)  Calculator or device with calculator function;  Sterile bowl;  Paper copy of Operative Worksheets;  2 packages Covidien™ Vistec™ X-ray Detectable Sponges, 16-Ply, 4" x 4" (hereinafter referred to as gauze)  1 liter of warm saline; and  Envelopes for randomization. 
b. Tare calibrated scale.
 
c. Pre-weigh packaged, sterile gauze in grams to 3 decimal places (0.001 g increments) and record.
 
d. In a manner that will not compromise sterility, introduce pre-weighed and non-weighed sterile gauze to the sterile field until ready for use.
 
e. Visually inspect the sealed packages of devices. If either package has been previously opened or damaged, discard and replace with a new package.
 
f. Pre-weigh packaged Study Devices in grams to 3 decimal places (0.0001 g increments) and record.

2	
a. Perform conventional methods for hemostasis, including but not limited to, pressure and ligature.
 
b. Blot bleeding site with clean non-weighed gauze and gentle pressure to remove blood and any other fluid from the study site.
 
c. Ligate any remaining vessels or suture holes >= 2 mm diameter.
	

	Investigator	Coordinator/Surgical Associate
3	
a. Inspect the bleeding site. Determine whether additional hemostatic measures need to be performed by application of a topical hemostat agent.
	
4	
a. Using a millimeter-incremented tool, measure the 2 longest perpendicular distances (cm) of the bleeding site.
	
a. Record the 2 longest perpendicular distances of the bleeding site.
 
b. Multiply those two values to calculate the Anatomic Site.
 
c. Add 1cm to each of the 2 recorded longest perpendicular distances of the bleeding site and multiply those two values to calculate Anatomic Application Site.
 
d. Verify eligibility of Anatomic Site and Anatomic Application Site based on calculated surface areas with intraoperative inclusion/exclusion criteria before proceeding.

5	
a. Blot bleeding site with clean non-weighed gauze and hold gentle pressure for 10 seconds to remove blood and any other fluid from the study site.
 
b. Have at hand, a stack of two gauze from pre-weighed packaged gauze (herein referred to as pre-weighed gauze).
	
6	
a. Immediately place two pre-weighed, gauze onto the bleeding site and hold them in place with gentle uniform pressure (enough to capture all the blood without deforming the gauze or the tissue) until blood is seen on top layer or for 10 seconds whichever occurs first using the timing device.
	
a. Start Timing device (seconds) when pre-weighed gauze contacts the bleeding site.
 
b. Stop timing device and remove gauze from bleeding site at 10 seconds or when surgeon sees blood on the top layer of the gauze, whichever occurs first.

7		
a. Tare pre-calibrated scale. Weigh unused gauze, gauze packaging, and blood-stained gauze (in grams, to 3 decimal places) and record.

	Investigator	Coordinator/Surgical Associate														
8	
a. Identify verbal description of bleeding site (a-f).
 
a. A score of 0 denotes no active bleeding. The surgical field is completely dry with no blood or the surgical field is stained with blood, but this blood is completely stagnant.
 
b. A score of 1 denotes oozing. The rate of bleeding is slow. This is what one may expect from capillary, venous, or arteriolar bleeding.
 
c. A score of 2 denotes slight bleeding. The rate of bleeding is slightly faster than oozing. There is no pulsatile flow present. This is what one may expect from capillary, venous, or arteriolar bleeding.
 
d. A score of 3 denotes moderate bleeding. There may be a weak pulsatile flow present. If there is a pulsatile flow, the rate of blood flow is similar to the rate of flow for a score of 2. If there is no pulsatile flow, the rate of blood flow is faster than slight bleeding.
 
e. A score of 4 denotes severe bleeding. For the most part, pulsatile flow is present. If there is no pulsatile flow, then the rate of blood flow is extremely rapid.
 
f. A score of 5 denotes life-threatening bleeding. A strong pulsatile flow is always present and the rate of blood flow is extremely rapid.
	
b. Calculate (2 significant digits after the decimal) Bleeding Flux [$\text{g}/(\text{cm}^2 \cdot \text{s})$] = [(blood mass collected(g))/ [Anatomic Site (cm^2) · time gauze held (s)]], record on Operative Worksheet 2.
 
If bleeding flux is $> 0.000040[\text{g}/(\text{cm}^2 \cdot \text{s})]$ and $\leq 0.013[\text{g}/(\text{cm}^2 \cdot \text{s})]$ enroll measured bleeding area; if bleeding flux is <0.000040 or $> 0.013[\text{g}/(\text{cm}^2 \cdot \text{s})]$, exclude bleeding site.
 
  
 Bleeding Severity Score	Bleeding Flux [$\text{g}/(\text{cm}^2 \cdot \text{s})$]	
   
 0=No Bleeding	0-0.000040	
 
 1=Ooze	$>0.000040-0.0056$	
 
 2=Slight Bleeding	$>0.0056-0.013$	
 
 3=Moderate Bleeding	$>0.013-0.041$	
 
 4=Severe Bleeding	$>0.041-0.063$	
 
 5=Life-Threatening Bleeding	>0.063	
  
	Bleeding Severity Score	Bleeding Flux [$\text{g}/(\text{cm}^2 \cdot \text{s})$]	0=No Bleeding	0-0.000040	1=Ooze	$>0.000040-0.0056$	2=Slight Bleeding	$>0.0056-0.013$	3=Moderate Bleeding	$>0.013-0.041$	4=Severe Bleeding	$>0.041-0.063$	5=Life-Threatening Bleeding	>0.063
Bleeding Severity Score	Bleeding Flux [$\text{g}/(\text{cm}^2 \cdot \text{s})$]															
0=No Bleeding	0-0.000040															
1=Ooze	$>0.000040-0.0056$															
2=Slight Bleeding	$>0.0056-0.013$															
3=Moderate Bleeding	$>0.013-0.041$															
4=Severe Bleeding	$>0.041-0.063$															
5=Life-Threatening Bleeding	>0.063															
9	
a. Confirm all Intraoperative eligibility criteria. If subject is eligible, continue to Randomization.
	
a. Record confirmation of intraoperative eligibility.
														
10		
Prepare RSD Accordingly PerCLOT Preparation
 
1. Remove the applicator from the package. Remove the granule dispenser (bellows) from its package. Remove the cap using a counter-clockwise turning motion (Fig.1). Connect the bellows firmly to the end of the applicator handle (Fig. 2). The system is now ready for use (Fig. 3). (Fig. 4).
 
 
  
Fig. 1
 
 
  
Fig. 2
 
 
  
Fig. 3
 
 
  
Fig. 4
 
 
 
Arista Preparation
 
1. Remove the applicator cap using a bending and twisting motion.
														
12		
a. Record Randomized Study Device (RSD) identifier number.
														
13		
a. Introduce RSD (two 5g bellows) to sterile field.
														

	Investigator	Coordinator/Surgical Associate
14	
 a. Before applying the RSD, have at hand: (1) a stack of two sterile non-weighed gauze and (2) warm sterile saline. b. Apply RSD, according to respective instructions for use. 	
 a. Prepare 700 cc of warm saline for irrigation

Device-Specific Application Instructions (INVESTIGATOR USE ONLY)

	PerClot	Arista
15	
 a. Remove all excess blood from the intended site by blotting, wiping, or suctioning. Identify and expose the source of bleeding of the wound. Ensure surface to which hemostat is being applied is dry and free from blood/fluid prior to application. Removing excess blood is critical to maximizing the hemostatic performance as it allows the granules direct contact with the site and source of active bleeding. b. Pump the granule dispenser/bellows to deliver granules directly to the site of bleeding. Immediately apply a liberal amount of PerClot granules directly to the source of bleeding. Thoroughly cover the lesion with a layer of granules 3-4 mm in thickness. Extend the product application to approximately 0.5cm (or 5mm) beyond the edge of the site of bleeding. The amount of application will depend upon the size of the bleeding site, contour of the bleeding site, and severity of bleeding. The amount of PerClot granules applied will increase with increasing size of the bleeding site and severity of bleeding. 
 1. The PerClot granules will help identify the source(s) of active bleeding; granules over source(s) of active bleeding will stain with blood. Additional granules should be applied to these area(s). 2. When managing deep wounds, the applicator tip must be as close to the source of the bleeding as possible without contacting blood. 	
 a. Blot, wipe, or suction the bleeding tissue. It is important to remove excess blood so that Arista may be applied immediately and directly to the site of active bleeding. b. Immediately apply a liberal amount of Arista at the site of bleeding within the wound, as close to the source of bleeding as possible, completely covering the wound. Deep wounds may require equally deep application of Arista. To minimize occlusion of the tip, pressure should be applied to deliver as the applicator enters the wound. 
Do not apply more than the entire contents of up to two 5 gram bellows of Arista per subject.

	Investigator	Coordinator/Surgical Associate
	
CAUTION: Avoid contacting the applicator tip with blood as this may occlude the applicator. If this occurs, replace applicator tip, if available. If this occurs, and a replacement tip is not available, use a stylus to reestablish the delivery pathway by inserting the stylus through the blocked area. Do not attempt to trim the applicator tip.
 
Do not apply more than the entire contents of up to two 5 gram bellows of PerClot per subject.
	
Discontinue Device-Specific Instructions.		
Continue with the remaining Operative Steps for both PerClot and Arista.		
16	
a. Immediately following application, cover treated site with two clean, sterile, non-weighed gauze. Hold and apply gentle uniform pressure to gauze pads until 5 minutes and 0 seconds.
	
a. Start Timing Device.
 
b. Weigh RSD packaging on a calibrated scale and record.
 
c. Weigh used RSD bellow(s) and applicator tip(s) on a calibrated scale and record.
 
d. Calculate weight of hemostat applied by subtracting the mass measured in steps 16b and 16c from the mass of the pre-weighed packaged study device to which the subject was randomized.

17	
a. At 5 minutes, gently remove gauze by fully saturating gauze with saline and slowly peeling them off as not to dislodge hemostat mass.
	
a. Record actual time at 5 minute assessment.

18	
a. Assess for hemostasis (complete cessation of bleeding).
 
b. Assess for dislodgement of RSD and if primary reason for any observed bleeding.
	
a. Record 5 minute assessment.
 
b. Record if dislodgement of RSD was observed and if primary reason for any observed bleeding.

19	
a. Cover treated site with two clean, sterile, non-weighed gauze. Hold and apply gentle uniform pressure to gauze until 7 minutes and 0 seconds.
	
20	
a. At 7 Minutes, gently remove gauze by fully saturating gauze with saline and slowly peeling them off as not to dislodge hemostatic mass.
	
a. Record actual time at 7 minute assessment.

21	
a. Assess for hemostasis (complete cessation of bleeding).
 
b. Assess for dislodgement of RSD and if primary reason for any observed bleeding.
	
a. Record 7 minute assessment.
 
b. Record if dislodgement of RSD was observed and if primary reason for any observed bleeding.

	Investigator	Coordinator/Surgical Associate
22	
a. If hemostasis was achieved at 7 minutes observe site until 12 minutes to assess maintenance of hemostasis. After the 12 minute observation period, remove excess RSD carefully by gentle saline irrigation and aspiration. Cardiac patients who have received PerClot only: Following the application of PerClot for epicardial bleeding within the pericardial cavity and achievement of hemostasis, the pericardial cavity should be rinsed with up to 70cc of fluid per 1 gram of PerClot in order to ensure removal of excess particles.
 
b. If hemostasis was not achieved at 7 minutes or if hemostasis was not maintained at any point during the additional 5 minute observation period or beyond (12 minute post-application), the surgeon may employ alternative means of achieving hemostasis.
	
a. If applicable, record actual time at additional 5 minute assessment (12 minutes post-application). If breakthrough occurs, record actual time of breakthrough.
 
b. Record any alternative means for achieving hemostasis.
 
c. Record the volume of fluid used to rinse away excess RSD and the estimated amount of study device remaining following irrigation.

23	a. Estimate the amount of RSD left in the patient in relation to the original amount applied (percentage) after careful and complete saline irrigation and aspiration of excess material, if applicable.	
24		
a. Return not assigned RSD to investigational drug pharmacy or accountability center and any remaining assigned RSD/packaging. Used RSD packaging is to be kept throughout patient study duration.

25	
a. Prior to surgical closure, verify hemostasis maintenance. If hemostasis is not maintained, the surgeon may employ alternative means of achieving hemostasis.
	
a. Record verification of hemostasis maintenance.
 
b. Record any alternative means for achieving hemostasis, if applicable.

RESUME all Post-Operative Safety and Data Instructions.

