6.4.3.4 Hemostat Application

The prescribed hemostatic agent will be applied according to the respective product Instructions for Use. Any device malfunctions will be recorded on the Device Malfunctions eCRF using FDA CDRH (Center for Devices and Radiological Health) Event Reporting nomenclature.²³ This will be a single-blinded trial. The subjects will be blinded as to the hemostatic treatment received. Unblinding will be permitted after a subject has completed his or her 6 week follow-up visit evaluation.

The anatomic site is defined as the approximate surface area of bleeding site, measured by multiplying the greatest perpendicular distances of the bleeding site. The anatomic application site is defined as the approximate surface area of the target application site, measured by adding one (1) centimeter to both greatest perpendicular distances of the bleeding site and multiplying the two values. The anatomic site and anatomic application site must meet all intraoperative eligibility criteria noted in Section 6.4.3.2. The anatomic site must not exceed 25cm². The anatomic application site must not exceed 47cm². Anatomic site and anatomic application site will be calculated and documented for the bleeding site on the Operative eCRF.

NOTE: The actual resection site may be larger than the anatomic site and/or anatomic application site (e.g., a liver resection site may be 5 inches by 4 inches, however you will only be allowed to evaluate investigational product on a 25cm² anatomic site).

The investigator will be allowed to use the entire contents of up to two 5 gram bellows of PerClot per investigational subject. Each box of PerClot supplied will contain five separate packages. Only two 5 gram bellows (packages) can be used per subject. Sites will be instructed to bring two packages of PerClot and two packages of the control product into the operating room on the day of the surgery. Application of investigational product will be addressed during investigator training. The exact amount of investigational product applied will be determined by weighing the device(s) before and after use.

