6.4.3.5 Intraoperative Evaluations and Assessment of Hemostasis

All subjects will undergo the same intraoperative investigation evaluations unless otherwise stated. Intraoperative is defined as the time interval from when the subject enters the surgical suite until the subject exits the surgical suite. Hemostatic evaluation time points will be measured on a continuum with time zero being the time of hemostat application. The treated bleeding site will be observed and evaluated at each of the pre-defined time points regardless of when hemostasis is achieved. For example, if hemostasis is achieved at 5 minutes, the surgeon will still evaluate the application site at 7 minutes to ensure that hemostasis has been maintained. If hemostasis is observed at 7 minutes, an assessment will be made to ensure hemostasis maintenance for an additional 5 minutes (12 minutes post-application) and again just prior to surgical closure.

Success/failure criteria will be defined as follows:

- If the surgeon visually observes complete cessation of bleeding, this will be considered successful hemostasis;
- If the surgeon visually observes bleeding egressing from the RSD, this will be considered a failure of hemostasis;

If hemostasis is not achieved at 7 minutes after test or control hemostat application, the surgeon may use alternative means necessary to achieve hemostasis (i.e., other approved and marketed hemostatic devices for the applicable therapeutic area). Additionally, if hemostasis is achieved at 7 minutes after test or control hemostat application, but is not maintained at any point during the additional 5 minute observation period (12 minutes post-application) or bleeding is observed at the target application site just prior to closure, the surgeon may use alternative means necessary to achieve hemostasis (i.e., other approved and marketed hemostatic devices for the applicable therapeutic area). Any alternative

means used to achieve hemostasis will be documented. The test or control hemostat will not be allowed to be re-applied after the 7 minute hemostatic evaluation time point.

A sample Operative Worksheet is attached as Appendix F; this worksheet will assist in the collection of intraoperative data and will act as the source document for intraoperative evaluations. All intraoperative data will be recorded.

The following intraoperative parameters will also be collected after the 7 minute hemostasis endpoint and prior to closure:

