*If yes, please complete the Blood Modifiers / Insulin or Blood Sugar Lowering Medications Form.
Refer to Appendices L & K For Complete List.*

Operative DRAFT Form
Form 3E

Form completed by: _____
Date form completed: ___ / ___ / ___

PerClot® - The C.L.O.T. Investigation

Subject Initials: Subject Number: Visit Type: 3 Intraoperative

TOTAL HEMOSTATIC PRODUCT APPLIED

38. Number of bellows used: 1 239. Verify mass of 2 packaged 5g bellows before application – RANDOMIZED: . grams40. Mass of packaging: . grams41. Mass of bellows and applicator tips after application: . grams42. Mass of hemostat applied: . grams

[(Value from Question #41) – (Value from Question #42) – (Value from Question #43)]

43. Time of Application:
HH:MM:SS (24-hour clock) : : 0 N/A

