4.6 Covariate Analysis

Covariate analyses will be performed to assess the association with certain study parameters on the primary efficacy endpoint. These models will be fit using logistic regression, measuring the odds of primary efficacy success. All models will include treatment group as a covariate. Covariates found to be significant at a 0.1 alpha level in the univariate assessment will be included in a multivariable model. After the multivariable model is fit, covariates will remain in the final multivariable model if they maintain significance at a 0.1 alpha level. For both univariate and multivariate models, the model derived estimates (i.e. beta estimates) for the association with primary efficacy success will be displayed, along with the Type III p-values. An adjusted estimate of the difference between proportions and associated 95% confidence interval (treatment versus control) will be obtained from the multivariable model.

Covariate assessments may consist of, but are not limited to, the following variables:

- Demographic measures such as age, gender, ethnicity, and BMI;
- Medical history;
- Therapeutic area;

- Use of blood modifiers or products known to affect bleeding (including aspirin and colloids);;
- Administration of blood products;
- Fluids administered (including colloids and crystalloids);
- Surface area of the anatomic site;
- Initial bleeding severity (as continuous measure);
- Indication for surgery;
- Complete blood count and coagulation status;
- Complement C3;
- Smoking history;
- Use of oral contraceptives;
- Diabetes;
- Presence of any malignancies;
- Amount of hemostat applied;
- Core body temperature;
- Level of glycosylated hemoglobin;
- Other hemostatic efforts made;
- Procedure type;
- NNIS risk index;
- Blood glucose at randomization;
- Blood glucose within 1 hour of device application;
- American Society of Anesthesiologists Classification;
- Total operative time;
- Placement of wound drain;
- Drainage volume within 24 hours postoperatively;
- Total drainage volume;
- Total drainage duration; and
- Volume of fluid used to rinse away excess study device.

In the event that a covariate is significant at the 0.05 alpha level in the univariate assessment, an additional model will be fit to test for an interaction effect of treatment and that covariate.

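### Step 16 of the Operative Steps does not weigh back an unused bellows; followed literally, it overstates applied mass by about 5 g plus container when one bellows is used

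*Protocol*

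**What the plan says.** Protocol section 6.4.3.4 sets the aim: "The exact amount of investigational product applied will be determined by weighing the device(s) before and after use".

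The procedure is in Appendix N. Step 1 has the team prepare and pre-weigh "Study Devices (2 packaged 5g bellows of PerClot and 2 packaged 5g bellows of Arista" (the list item continues). Step 13 brings both bellows of the assigned device to the sterile field. Step 16b weighs the packaging. Step 16c reads "Weigh used RSD bellow(s) and applicator tip(s) on a calibrated scale and record". Step 16d reads "Calculate weight of hemostat applied by subtracting the mass measured in steps 16b and 16c", the subtraction being made from the pre-weighed packaged device of the assigned arm. Step 24 sends back "any remaining assigned RSD/packaging" and does not ask for it to be weighed.

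The Operative Form (Appendix E) and the Operative Worksheet (Appendix F) carry the same items. Section 6.4.3.5 makes the worksheet the source document for intraoperative data.

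- Item 38: bellows used, one or two.
- Item 39: "Verify mass of 2 packaged 5g bellows before application", for the randomized device.
- Item 40: packaging mass.
- Item 41: mass of bellows and tips once the product has been applied. The word used does not appear.
- Item 42: mass of hemostat applied. Its printed formula is item 41 minus item 42 minus item 43.
- Item 43: clock time of application.

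SAP section 4.6 and protocol section 6.6.11 list "Amount of hemostat applied" among the variables that may be assessed as covariates for the primary endpoint.

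**The concern.** The two sides of the mass balance do not cover the same objects. The starting mass always includes two filled, packaged bellows. The subtraction in step 16 covers only packaging and what was used. If one bellows is enough, the other stays in the result and is counted as applied.

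The same appendix handles gauze correctly: step 7 puts the unused gauze back on the scale with its packaging and the blood-stained gauze. The device steps have no counterpart.

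Item 41 is worded more broadly than step 16c, so two sites can treat the same event differently. The formula printed for item 42 cannot settle the matter, because it refers to itself and to a clock time. Step 16d is therefore the only calculation in the documents that can be carried out.

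At stake is the recorded amount applied. Under SAP 4.6 a covariate significant at the 0.1 level univariately enters a multivariable model, and an adjusted treatment difference is taken from that model. A variable with an offset tied to the number of bellows used, and possibly to site, is a poor candidate for it.

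**Working it through.** The documents state no figure for applied mass, so there is none to reproduce. The check is a mass balance.

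**Inputs**

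- F = 5 g, nominal fill per bellows (Appendix N step 1; item 39).
- B = mass of one bottle, cap and tip. Not in the documents; varied from 0 to 20 g as an assumption.
- P = packaging mass per unit. Not in the documents; varied from 0 to 10 g as an assumption.
- x = mass truly applied.
- Starting mass = 2(F + B + P).

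**One bellows used, step 16 followed literally**

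(a) Packaging of both units subtracted:
2(F + B + P) − 2P − (F + B − x) = x + F + B.

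(b) Packaging of the opened unit only subtracted:
2(F + B + P) − P − (F + B − x) = x + F + B + P.

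The overstatement is F + B or F + B + P, hence at least 5 g at nominal fill.

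**One bellows used, other readings**

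(c) Item 41 taken to cover both bellows:
2(F + B + P) − 2P − [2(F + B) − x] = x.

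(d) Unused unit still sealed and weighed with the packaging at step 16b:
2(F + B + P) − [P + (F + B + P)] − (F + B − x) = x.

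Both give the true mass.

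**Two bellows used**

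2(F + B + P) − 2P − [2(F + B) − x] = x. No error.

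**Recorded mass (g) when one bellows is used**

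| B, P (assumed) | True x | (a) | (b) | (c), (d) |
|---|---|---|---|---|
| 0, 0 | 1 | 6 | 6 | 1 |
| 0, 0 | 3 | 8 | 8 | 3 |
| 0, 0 | 5 | 10 | 10 | 5 |
| 5, 5 | 3 | 13 | 18 | 3 |
| 10, 5 | 3 | 18 | 23 | 3 |
| 20, 10 | 3 | 28 | 38 | 3 |

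**Item 42 references.** The three masses that step 16d needs are items 39, 40 and 41. The printed references are 41, 42 and 43.

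**Would a range check find it?** A ceiling of 10 g (two bellows) flags a literal record under (a) only if x + 5 + B > 10, that is, x + B > 5. A ceiling of 5 g × item 38 flags it if x + 5 + B > 5, that is, whenever x + B > 0 before any fill tolerance. The second check catches the 8 g record in the table; the first does not.

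**The case against.** The best reply is that the source worksheet governs what is recorded, and item 41 does not say used. Coming after an item that weighs two bellows, it can fairly be read as weighing the same two afterwards. Section 6.4.3.4 also speaks of weighing the device or devices before and after. Both bellows are on the sterile field after step 13. Used in step 16c might mean assigned, as opposed to the unassigned product of step 24, and packaging in step 16b is not defined. Any site taking one of these readings records the right mass. In addition, the forms are samples whose live layout may differ, items 38 to 41 are stored separately, and all data are source-verified.

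This stands as far as it goes. It shows that the error is not certain at any given site. It does not show that the documents tell sites to weigh the unused bellows, and it leaves step 16 and item 41 in disagreement.

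Several stronger readings are tempting and not supported:

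- *Every one-bellows subject is misrecorded.* Item 41 allows correct recording. The documents also give no share of one-bellows subjects, so no count can be stated.
- *This is the only exposure measure.* The number of bellows, the estimated percentage remaining and the rinse volume are also collected.
- *It is the check on the two-bellows limit.* That limit is a count, captured by item 38.
- *It drives the pericardial rinse.* The rinse text sets an upper limit per gram, and no step ties it to item 42.
- *It reverses an exposure-response for glucose or swelling.* No such analysis is planned.
- *Powder added after the weighing is missed.* Section 6.4.3.5 says "The test or control hemostat will not be allowed to be re-applied after the 7 minute hemostatic evaluation time point", but no step provides for re-application before then; extra granules belong to step 15, before the weighing.

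**Conclusion.** The point holds for step 16 as written. Followed literally, it overstates a one-bellows subject's applied mass by the 5 g nominal fill plus the container, and plus one packaging mass if only the opened unit's packaging is subtracted. For two-bellows subjects the error is zero. Because item 41 can be read to include both bellows, recorded values for identical use can lie at least 5 g apart between sites. The item 42 references are wrong on either reading.

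The 5 g rests on nominal fill. Anything above it depends on container and packaging masses that the documents do not give.

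The effect is confined to amount applied, as a recorded quantity and a candidate covariate. Trial success (SAP 4.2.3) rests on the difference in 7-minute hemostasis proportions, which does not use this variable; the non-inferiority test and the sample size do not use it either. The correction should be made before amount applied is summarized or modeled.

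**What to change.** 1. Reword step 16c–d and item 41 alike, in Appendices E, F and N, so that any unused assigned bellows, with its tip and pouch, is weighed back and subtracted, as step 7 does for gauze. Alternatively, pre-weigh each packaged bellows separately and start only from those opened.
2. Correct the item 42 formula to item 39 − item 40 − item 41.
3. Add an edit check that item 42 does not exceed 5 g × item 38 plus a stated fill tolerance.
4. Query existing records with item 38 = 1 to establish what was weighed. Where only the opened unit was weighed, an approximate value is half of item 39, minus one unit's packaging, minus item 41: (F + B + P) − P − (F + B − x) = x. It is approximate because half of item 39 stands in for the opened unit's own pre-weight.

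The cost is a wording change, at most a few form fields, one edit check, one extra weighing on a balance already in the room, and a query round limited to one-bellows subjects.
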